9.5.4.5 Breaking the Blind

Not applicable.

9.5.4.6 Regulatory Reporting of Adverse Events

Adverse events will be reported by the sponsor or a third party acting on behalf of the sponsor to regulatory authorities in compliance with local and regional law and established guidance. The format of these reports will be dictated by the local and regional requirements.

All studies that are conducted within any European country will comply with European GCP Directive 2005/28/EC and Clinical Trial Directive 2001/20/EC. All SUSARs will be reported, as required, to the competent authorities of all involved European member states.

9.5.5 Completion/Discontinuation of Subjects

The investigator may withdraw the subject from the study at any time for safety or administrative reasons. A subject may elect to discontinue the study at any time for any reason. All subjects who discontinue the study are to complete the study's early

discontinuation procedures indicated in the Schedule of Visits and Procedures/Assessments (Table 4).

The investigator will promptly explain to the subject involved that the study will be discontinued for that subject and provide appropriate medical treatment and other necessary measures for the subject. A subject who has ceased to return for visits will be followed up by mail, phone, or other means to gather information such as the reason for failure to return, the status of treatment compliance, the presence or absence of AEs, and clinical courses of signs and symptoms.

Subjects who discontinue early from the study will be discontinued for 1 of these primary reasons: AE(s), lost to follow-up, subject choice (ie, subject chooses to discontinue from the treatment but is willing to participate in the Follow-Up portion of the study), progression of disease, withdrawal of consent (ie, subject no longer wishes to participate in the study and be contacted), pregnancy, sponsor discontinuation of the study, or other. In addition to the primary reason, the subject may indicate 1 or more secondary reason(s) for discontinuation. Study disposition information will be collected on the Subject Disposition CRF. Subjects will be judged as lost to follow-up only if they cannot be reached after 3 documented attempts (at least 1 week apart) by the site to contact them.

9.5.6 Abuse or Diversion of Study Drug

Not applicable.

9.5.7 Confirmation of Medical Care by Another Physician

The investigator will instruct subjects to inform site personnel when they are planning to receive medical care by another physician. At each visit, the investigator will ask the subject whether he/she has received medical care by another physician since the last visit or is planning to do so in the future. When the subject is going to receive medical care by another physician, the investigator, with the consent of the subject, will inform the other physician that the subject is participating in the clinical study.

9.6 Data Quality Assurance

This study will be organized, performed, and reported in compliance with the protocol, SOPs, working practice documents, and applicable regulations and guidelines. Site audits will be made periodically by the sponsor's or the CRO's qualified compliance auditing team, which is an independent function from the study team responsible for conduct of the study.

9.6.1 Data Collection

Data required by the protocol will be collected on the CRFs and entered into a validated data management system that is compliant with all regulatory requirements. As defined by ICH guidelines, the CRF is a printed, optical, or electronic document designed to record all of the protocol-required information to be reported to the sponsor on each study subject.

Data collection on the CRF must follow the instructions described in the CRF Completion Guidelines. The investigator has ultimate responsibility for the collection and reporting of all clinical data entered on the CRF. The investigator or designee as identified on Form FDA 1572 must sign the completed CRF to attest to its accuracy, authenticity, and completeness.

Completed, original CRFs are the sole property of Eisai and should not be made available in any form to third parties without written permission from Eisai, except for authorized representatives of Eisai or appropriate regulatory authorities.

9.6.2 Clinical Data Management

All software applications used in the collection of data will be properly validated following standard computer system validation that is compliant with all regulatory requirements. All data, both CRF and external data (eg, laboratory data), will be entered into a clinical system.

The Data Management Plan defines and documents the procedures necessary to ensure data quality. These activities must be followed to ensure that data are properly entered, validated, coded, integrated, reconciled, and reviewed.

9.7 Statistical Methods

All statistical analyses will be performed by the sponsor or designee after the study is completed and the database is locked and released. Statistical analyses will be performed using SAS software or other validated statistical software as required. Details of the statistical analyses will be included in a separate statistical analysis plan (SAP).

9.7.1 Statistical and Analytical Plans

The statistical analyses of study data are described in this section. Further details of the analytical plan will be provided in the SAP, which will be finalized before database lock.

9.7.1.1 Study Endpoints

9.7.1.1.1 PRIMARY ENDPOINT

- The primary efficacy endpoint is ORR as determined by investigator review, using RECIST 1.1. ORR is the proportion of subjects who have best overall response (BOR) of CR or PR.

9.7.1.1.2 SECONDARY ENDPOINTS

- Twelve-week PFS is the percentage of subjects in the analysis population who remain alive and progression-free at 12 weeks.
- Six-month OS is defined as the percentage of subjects in the analysis population who are alive at 6 months. It will be estimated using the KM method.
- Median PFS and median OS.

9.7.1.1.3 EXPLORATORY ENDPOINTS

- CBR is the proportion of subjects who have best overall response of CR or PR or durable SD. Stable disease must be achieved at ≥ 23 weeks after first lenvatinib administration to be considered durable SD.
- DCR is the proportion of subjects who have best overall response of CR, PR or SD. Stable disease must be achieved at ≥ 5 weeks after the first lenvatinib administration to be considered BOR.
- DOR is defined as the time from the date that the criteria are met for CR or PR, whichever is recorded first, to the date that PD is objectively documented or death, whichever occurs first.
- Evaluate the association of tumor and blood biomarkers with clinical outcomes, including efficacy.

All above primary, secondary and exploratory endpoints based on tumor measurement will be assessed according to RECIST 1.1.

9.7.1.2 Definitions of Analysis Sets

Full Analysis Set (FAS) will include all subjects who received at least one dose of lenvatinib. The FAS will be the population for the safety analysis. Some selected efficacy endpoints will also be summarized in the FAS.

Evaluable Analysis Set (EAS) will include FAS subjects with histological diagnosis of ATC that is confirmed by central pathology review. The EAS will be the primary population for the efficacy analysis.

9.7.1.3 Subject Disposition

The number of subjects enrolled, treated, prematurely discontinued from study treatment (defined as those who discontinued study treatment due to any reason except for progressive disease) and those with major protocol deviations will be counted. The primary reason for study drug discontinued will be summarized according to the categories in the CRF. The end of study status (alive, death, withdrew consent or lost to follow-up) at the data cutoff date will be summarized using the data from the survival follow-ups.

Major protocol deviations will be summarized and listed by each category.

9.7.1.4 Demographic and Other Baseline Characteristics

Demographic and other baseline characteristics will be summarized in both Full Analysis Set and Evaluable Analysis Set, using descriptive statistics. Continuous variables include age, weight, vital signs, time since ATC diagnosis; categorical variables include sex, age group, race, disease stage, ECOG-PS, prior line of chemotherapy for ATC and region.

9.7.1.5 Prior and Concomitant Therapy

Concomitant medications will be assigned an 11-digit code using the World Health Organization Drug Dictionary drug codes. Concomitant medications will be further coded to the appropriate ATC code indicating therapeutic classification. Prior and concomitant medications will be summarized and listed by drug and drug class in the CSR for this protocol. Prior medications will be defined as medications that stopped before the first dose of study drug. Concomitant medications will be defined as medications that (1) started before the first dose of study drug and were continuing at the time of the first dose of study drug, or (2) started on or after the date of the first dose of study drug up to 28 days after the subject's last dose. A listing of prior and concomitant medications will be included in the CSR of this protocol.

9.7.1.6 Efficacy Analyses

9.7.1.6.1 PRIMARY EFFICACY ANALYSIS

In this population, ORR in the historical control is assumed to be approximately 10% based on recent trials. The ORR in this trial is estimated as 27%, which is deemed a clinical meaningful improvement. Hence, the null and alternative hypotheses are set as follows:

$$H_0: \text{ORR} = 10\%$$

$$H_a: \text{ORR} \geq 27\%$$

A binomial exact test will be performed for hypothesis testing in the Evaluable Analysis Set. If the obtained p-value is less than or equal to 0.025, it will be concluded that the single agent lenvatinib statistically significantly increases ORR compared with historical control. Therefore, the superiority of single agent lenvatinib will be demonstrated.

Clopper Pearson 95% CI of ORR will also be constructed to assess the precision of the rate estimate.

9.7.1.6.2 SECONDARY EFFICACY ANALYSES

PFS is defined as the time from the date of beginning of lenvatinib administration to the date of first documentation of disease progression or death, whichever occurs first.

PFS censoring rule will follow FDA Guidance for Industry, Clinical Trial Endpoints for Approval of Cancer Drugs and Biologics (2007).

Subjects who have a clinical determination of progression should undergo an MRI, if possible, to correlate radiographic findings with the clinical findings. If a clinical determination of progression for a subject is confirmed by an MRI scan, the date of the MRI scan will be considered as the progression date for that subject. Data for subjects without disease progression or death at the time of analysis will be censored at the time of the last tumor assessment. Data for subjects who are lost to follow-up prior to documented disease progression will be censored at the last tumor assessment date when the subject is known to

be progression-free. Data for subjects who start to receive new anticancer therapy will be censored at the last tumor assessment date prior to the introduction of new therapy. More details will be given in the SAP.

A 12-week PFS of $\geq 70\%$ in single agent lenvatinib and 50% in the historical control (corresponding to a median PFS improvement of approximately 3 months assuming exponential distribution) are assumed in the hypothesis testing:

$$H_0: 12\text{-week PFS} = 50\%$$

$$H_a: 12\text{-week PFS} \geq 70\%$$

Kaplan-Meier (KM) method will be used to estimate 12-week PFS, along with the corresponding 95% CI constructed using Greenwood's formula ([Greenwood, 1926](#); [Collett, 1994](#)). The CI approach will be used to demonstrate the superiority of 12-week PFS in the single agent lenvatinib over historical control. If the lower bound is above 50%, it will be concluded that the single agent lenvatinib statistically significantly increases 12-week PFS compared with historical control.

Overall survival is defined as the time from the date of beginning of lenvatinib administration until date of death from any cause. Six-month OS is assumed to be approximately 44% in the historical control (corresponding to a median OS of approximately 5 months assuming an exponential distribution). Six-month OS and its 95% CI will be calculated using the same methods as described in the 12-week PFS analyses. If the lower bound of 95% CI for 6-month OS is above 44%, it will be concluded that the single agent lenvatinib statistically significantly increases 6-month OS compared with historical control.

Median PFS and median OS will be estimated using the KM method. Their 2-sided 95% CIs will be constructed with a generalized Brookmeyer and Crowley method ([1982](#)). KM estimates of PFS and OS will be plotted over time.

Secondary efficacy endpoints will be analyzed sequentially, as listed above.

9.7.1.6.3 EXPLORATORY EFFICACY ANALYSES

CBR, DCR, and DOR will be analyzed using the statistical methods as described above.

Tumor and blood biomarkers will be analyzed to assess the correlation with clinical endpoints, including efficacy. The analysis plan will be described in a separate report.

9.7.1.6.4 FORMAL ANALYSES

A formal analysis will be carried out approximately 6 months following the enrollment of the last subject. The timing of the formal analysis is chosen such that the secondary endpoints, 12-week PFS and 6-month OS, will be adequately described. The primary population for efficacy analysis is EAS. Efficacy and safety analysis will also be performed in FAS.

9.7.1.7 Pharmacokinetic, Pharmacodynamic, Pharmacogenomic, and Other Biomarker Analyses

9.7.1.7.1 PHARMACOKINETIC ANALYSES

Not applicable.

9.7.1.7.2 PHARMACODYNAMIC, PHARMACOGENOMIC, AND OTHER BIOMARKER ANALYSES

Exploratory analyses of tumor and blood biomarkers will be performed to assess the correlation with clinical endpoints, including efficacy, and reported separately. Details of these analyses may be described in a separate analysis plan.

9.7.1.8 Safety Analyses

Safety, using the FAS, will be assessed by monitoring and recording of all AEs including all CTCAE v4.03 grades (both increasing and decreasing severity), regular monitoring of hematology and clinical chemistry, urinalysis, regular measurement of vital signs, 12-lead ECGs, echocardiogram or MUGA scan results (only for subjects who had prior anthracyclines) including left ventricular ejection fraction and performance of PEs.

9.7.1.8.1 EXTENT OF EXPOSURE

Extent of exposure to study drug will be summarized descriptively as the number of cycles received (number and percentage of subjects), duration of exposure (days), cumulative total dose received per subject (mg), dose intensity (mg/day) and percent of planned dose received.

The number (percentage) of subjects requiring dose reductions, dose interruption, dose delay, and drug discontinuation due to AEs will be summarized. The cycle in which the first dose reduction/interruption occurred will be summarized using descriptive statistics. Frequency of reductions and dose interruptions will be summarized by categories.

Time to the first dose reduction (from 24 mg to 20 mg) is defined from the date of the first dose (24 mg) to the date of the first dose reduction (20 mg), or first dose interruption if subjects had dose interruption followed by dose reduction, or the date of drug discontinuation if AE was leading to it.

Subject data listings will be provided for all dosing records and for calculated summary statistics.

9.7.1.8.2 ADVERSE EVENTS

The AE verbatim descriptions (investigator terms from the CRF) will be classified into standardized medical terminology using Medical Dictionary for Regulatory Activities (MedDRA[®]). Adverse events will be coded to MedDRA (Version 17 or higher) lower level term closest to the verbatim term. The linked MedDRA preferred term (PT) and primary system organ class (SOC) are also captured in the database.

A TEAE is defined as an AE that had an onset date or a worsening in severity from baseline (pretreatment) on or after the first dose of study drug up to 28 days following study drug discontinuation. Only those AEs that were treatment emergent will be included in summary tables. All AEs, treatment emergent or otherwise, will be presented in subject data listings.

The incidence of TEAEs will be reported as the number (percentage) of subjects with TEAEs by SOC and PT. A subject will be counted only once by the highest severity grade according to CTCAE v4.03 within an SOC and PT, even if the subject experienced more than 1 TEAE within a specific SOC and PT. The number (percentage) of subjects with TEAEs will also be summarized by relationship to the study drug. Treatment-related AEs include those events considered by the investigator to be possibly or probably related to study treatment or with missing assessment of the causal relationship. Serious adverse events, deaths, TEAE with grade 3 or above, and TEAEs that led to treatment discontinuation, dose reduction or dose interruption will be summarized.

9.7.1.8.3 LABORATORY VALUES

Clinical laboratory (ie, hematology, serum chemistry and qualitative urinalysis) values will be evaluated for each laboratory parameter by subject. Abnormal laboratory values will be flagged and identified as those outside (above or below) the normal range. Reference (normal) ranges for laboratory parameters will be included in the CSR for this protocol. Descriptive summary statistics (eg, n, mean, standard deviation, median, minimum, maximum for continuous variables; n[%] for categorical variables) for laboratory parameters and their changes from baseline will be calculated. Laboratory values will be summarized by visit and by worst postbaseline visit.

Laboratory parameters that are graded in CTCAE (v4.03) will be summarized by CTCAE grade. In the summary of laboratory parameters by CTCAE grade, parameters with CTCAE grading in both high and low directions (eg, calcium, glucose, magnesium, potassium, sodium) will be summarized separately.

Please see [Appendix 7](#) for sponsor's grading of laboratory values.

9.7.1.8.4 VITAL SIGNS

Descriptive statistics for vital sign parameters (systolic and diastolic BP, heart rate, respiratory rate, temperature, weight) and changes from baseline will be presented by visit for all visits. Vital signs will be listed by subject and visit.

9.7.1.8.5 ELECTROCARDIOGRAMS

Electrocardiogram assessments were performed at Screening and End of Treatment visit. Descriptive statistics for ECG parameters and changes from baseline will be presented.

9.7.1.8.6 OTHER SAFETY ANALYSES

9.7.1.9 Other Analyses

Primary, secondary and exploratory endpoints will be summarized in the evaluable analysis set in which central confirmed ATC is required. In the analyses described above and any other sensitivity analysis, subjects with missing data will be considered as non-responders and will be included in the denominator when calculating ORR, DCR, and CBR. Non-responders will be excluded in the analysis of DOR.

Any other statistical/ analytical issues will be discussed in the SAP.

9.7.2 Determination of Sample Size

The sample size calculation was based on the assumed ORR of 27% in the trial as compared to 10% in the historical control. Using a binomial exact test, the power is 0.932 with 57 evaluable subjects to demonstrate statistical significance at a 1-sided alpha of 0.025. To evaluate the power in the secondary endpoint 12-week PFS, an exponential distribution assuming 12-week PFS being 70% was used to simulate PFS data. Censoring times were generated such that the average number of observed PFS events was approximately 45 in the 57 evaluable subjects. In the 5,000 simulation runs, the lower bound of 95% CI for PFS at 12 weeks was greater than 50% (historical control), 87.7% of the time. Hence, the power is 0.877 in demonstrating statistical superiority of the 12-week PFS in single agent lenvatinib. Similarly, approximately 35 observed OS events in 57 evaluable subjects yield a power of approximately 0.857 in demonstrating a statistically significant increase in 6-month OS over historical control. Assuming ATC confirmation rate is 75% in the enrolled subjects, approximately 76 subjects will need to be enrolled. Subjects deemed to have another diagnosis (not ATC) will be replaced for the purpose of efficacy analyses.

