The sample size calculation was based on the assumed ORR of 27% in the trial as compared to 10% in the historical control. Using a binomial exact test, the power is 0.932 with 57 evaluable subjects to demonstrate statistical significance at a 1-sided alpha of 0.025. To evaluate the power in the secondary endpoint 12-week PFS, an exponential distribution assuming 12-week PFS being 70% was used to simulate PFS data. Censoring times were generated such that the average number of observed PFS events was approximately 45 in the 57 evaluable subjects. In the 5,000 simulation runs, the lower bound of 95% CI for PFS at 12 weeks was greater than 50% (historical control), 87.7% of the time. Hence, the power is 0.877 in demonstrating statistical superiority of the 12-week PFS in single agent lenvatinib. Similarly, approximately 35 observed OS events in 57 evaluable subjects yield a power of approximately 0.857 in demonstrating a statistically significant increase in 6-month OS over historical control. Assuming ATC confirmation rate is 75% in the enrolled subjects, approximately 76 subjects will need to be enrolled. Subjects deemed to have another diagnosis (not ATC) will be replaced for the purpose of efficacy analyses.

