9 INVESTIGATIONAL PLAN

9.1 Overall Study Design and Plan

This is an open-label, single arm, multicenter, Phase 2 study in subjects with ATC.

A descriptive interim analysis, which requires the first 20 evaluable subjects, will be implemented in the study. If the number of responders is 3 or less ($ORR \leq 15\%$), the enrollment will be halted and the safety and efficacy data will be further evaluated before making the decision of stopping the study permanently. Otherwise, the enrollment will be continued to 57 evaluable subjects. Since early stopping is not expected, to minimize the impact of interim analysis to clinical study operation, enrollment will not be halted after the first 20 evaluable subjects while waiting for the interim analysis results. Therefore, there will be no enrollment gap for the interim analysis.

Subjects should have measurable disease according to RECIST 1.1.

This study consists of 3 Phases: a Pretreatment Phase (Screening and Baseline visits), a Treatment Phase (starting Cycle 1 Day 1 [C1D1]), and a Posttreatment Phase (End of Treatment visit and survival follow-up).

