9.7.3 Interim Analysis

One interim analysis will be performed after the first 20 evaluable subjects complete at least 2 tumor assessments or discontinue treatment due to any reason. The trial will be halted if the number of responders is 3 or less ($ORR \leq 15\%$). Since type I error calculation for the primary efficacy analysis does not factor in this descriptive interim analysis, the interim decision will not affect the overall type I error in the formal primary analysis. Further action regarding enrollment will be taken after evaluating other efficacy and safety outcomes in the treated subjects. The probabilities of not passing interim threshold are 0.87, 0.41, and 0.17 when underlying true ORR are 10%, 20%, and 27%, respectively.

The study team will define the datasets for the interim analysis. The study team will assess the impact of any issues such as unsolved data queries, missing data or data entry delays on

the interim results. The study statistician will perform the interim analysis, which includes calculating ORR per protocol.

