## 4 DETERMINATION OF SAMPLE SIZE

The sample size calculation was based on the assumed objective response rate (ORR), defined in Section 5.1) of 27% in the trial as compared to 10% in the historical control. Using a binomial exact test, the power was 0.932 with 57 evaluable subjects to demonstrate statistical significance at a 1-sided alpha of 0.025. To evaluate the power in the secondary endpoint 12-week PFS (defined in Section 5.1), an exponential distribution assuming 12-week PFS being 70% was used to simulate PFS data. Censoring times were generated such that the average number of observed PFS events was approximately 45 in the 57 evaluable subjects. In the 5,000 simulation runs, the lower bound of 95% confidence interval for PFS at 12 weeks was greater than 50% (historical control), 87.7% of the time. Hence, the power was 0.877 in demonstrating statistical superiority of the 12-week PFS in single agent lenvatinib. Similarly, approximately 35 observed OS events in 57 evaluable subjects yielded a power of approximately 0.857 in demonstrating a statistically significant increase in 6-month OS over historical control. Assuming ATC confirmation rate was 75% in the enrolled subjects, approximately 76 subjects would need to be enrolled. Subjects deemed to have another diagnosis (not ATC) would be replaced for the purpose of efficacy analyses.

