## 6 INTERIM ANALYSES

Per study protocol, one interim analysis was planned to be performed after the first 20 evaluable subjects complete at least 2 tumor assessments or discontinue treatment due to any reason. From the interim analysis the enrollment would be halted if the number of responders is 3 or less ( $ORR \leq 15\%$ ), and the safety and efficacy data would be further evaluated before making the decision of stopping the study permanently.

The study team would define the datasets for the interim analysis. The study team would assess the impact of any issues such as unsolved data queries, missing data or data entry delays on the interim results. The study statistician would perform the interim analysis, which would include calculating ORR per protocol.

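### The stated power of 0.932 assumes the trial always reaches 57 evaluable subjects; it falls to 0.80 if every interim halt is final

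*Protocol*

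**What the plan says.** Protocol 9.7.2 states the primary power: "Using a binomial exact test, the power is 0.932 with 57 evaluable subjects to demonstrate statistical significance at a 1-sided alpha of 0.025". The synopsis (Sample Size Rationale) repeats it, "the power is 0.932 with 57 evaluable subjects", and so does SAP 4, "the power was 0.932 with 57 evaluable subjects". None of the three mentions the interim analysis.

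Protocol 9.7.3 places one interim after the first 20 evaluable subjects have had at least two tumor assessments or have stopped treatment. The trial is halted at 3 or fewer responders. The same section gives the chance of this at true ORRs of 10%, 20% and 27%: "The probabilities of not passing interim threshold are 0.87, 0.41, and 0.17". SAP 6 has the same trigger: "From the interim analysis the enrollment would be halted if the number of responders is 3 or less".

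A halt does not end the trial automatically. Protocol 9.1 says that the safety and efficacy "data will be further evaluated before making the decision of stopping the study permanently", and 9.7.3 adds: "Further action regarding enrollment will be taken after evaluating other efficacy and safety outcomes in the treated subjects". Enrolment is not paused for the analysis itself: "enrollment will not be halted after the first 20 evaluable subjects while waiting for the interim analysis results".

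Protocol 9.7.3 and SAP 5.3.3 discuss what the interim does to type I error. Neither document says what it does to power.

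**The concern.** A reader will take 0.93 as the chance of a positive primary result if the true ORR is 27%. By the protocol's own figure, about one trial in six at that ORR meets the halt condition, and the plan allows such a trial to be stopped for good. Any stop that ends a trial which would have reached significance removes power, and 0.932 leaves no room for that.

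The two published figures cannot simply be subtracted. 0.932 − 0.17 = 0.762 is too low, because some halted trials would have failed anyway. The loss is the probability of meeting the halt condition and also reaching the final criterion had the trial continued, which the documents do not give. The people deciding what to do after a halt would need that number.

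**Working it through.** **Inputs.** Null ORR 10%, alternative 27%, 57 evaluable subjects, exact binomial test at one-sided 0.025 (protocol 9.7.1.6.1 and 9.7.2). Interim at 20 evaluable subjects, halt at 3 or fewer responders (protocol 9.7.3). Write b(k; n, p) for the binomial probability of exactly k responders among n.

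**1. The plan's own figures.**
- Critical value: P(X ≥ 10 | 57, 0.10) = 0.0548, and P(X ≥ 11 | 57, 0.10) = 0.0242. Significance therefore needs 11 of 57.
- Power: P(X ≥ 11 | 57, 0.27) = 0.9321, the stated 0.932.
- Halt: P(X ≤ 3 | 20, p) = 0.867, 0.411 and 0.170 at p = 10%, 20% and 27%, the stated 0.87, 0.41 and 0.17.

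All of these reproduce. The 0.932 is a single-stage figure with no interim in it.

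**2. Power that passes through the halt region.** For k responders among the first 20, the trial would go on to succeed with probability P(Bin(37, 0.27) ≥ 11 − k).

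| k of 20 | b(k; 20, 0.27) | P(success if continued) | Product |
|---|---|---|---|
| 0 | 0.0018 | 0.4145 | 0.0008 |
| 1 | 0.0137 | 0.5608 | 0.0077 |
| 2 | 0.0480 | 0.7021 | 0.0337 |
| 3 | 0.1065 | 0.8207 | 0.0874 |
| Total | 0.1700 | | 0.1296 |

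Given a halt, the chance of reaching 11 of 57 by continuing is 0.1296 / 0.1700 = 0.762. With exactly 3 responders it is 0.821.

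**3. Power at 27% by what follows a halt.** A stopped trial counts as not significant. On the first 20 subjects alone this must be so, since the critical value at n = 20 is 6.

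| After a halt | Power |
|---|---|
| No halt ends the trial | 0.932 |
| Permanent stop only at 1 or fewer | 0.924 |
| Permanent stop only at 2 or fewer | 0.890 |
| Half of halts final, regardless of count | 0.9321 − 0.5 × 0.1296 = 0.867 |
| Every halt final | 0.9321 − 0.1296 = 0.8025 |

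The last row also comes directly from the sum over k = 4 to 20 of b(k; 20, 0.27) × P(Bin(37, 0.27) ≥ 11 − k) = 0.8025.

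**4. Type I error.** The same sum at p = 0.10 gives 0.0156, against 0.0242 without stopping.

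**5. Subjects enrolled before a halt is called.** Because enrolment is not paused, a stopped trial would hold more than 20 subjects. The documents do not give the number. Assume 57 evaluable subjects over 18 months (about 78 weeks) and 12 weeks for two scans: 57 / 78 × 12 ≈ 9 more, so n = 29. The critical value is then 7. Testing the stopped trial at 29 gives 0.8025 plus the sum over k = 0 to 3 of b(k; 20, 0.27) × P(Bin(9, 0.27) ≥ 7 − k), which is 0.828. Type I error is 0.0174. With 5, 10 or 20 extra subjects instead of 9, power is 0.805, 0.815 or 0.868.

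**6. Responses not yet countable at the interim.** Steps 2 to 5 treat every eventual confirmed response among the first 20 as known at the interim, as the protocol's 0.17 also does. Confirmation takes at least 28 days (protocol 9.5.1.3.1, SAP 5.1.1), so a response first seen at the second scan might not count yet. As an illustration only, if each eventual response had a 90% or 80% chance of being counted, power with every halt final would be 0.73 or 0.64.

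**The case against.** The strongest reply is that nothing here is wrong. The power statement carries its own condition, 57 evaluable subjects. The interim is called descriptive, meeting the threshold leads to a review and not to termination, and quoting power without a non-binding look is a recognised convention. The 0.80 describes a rule the plan does not contain, and 0.087 of the 0.130 loss requires a permanent stop at exactly 3 responders. The 0.17 is already disclosed in the next section. The 0.80 is not a true lower bound either, given the uncertainty over which responses are countable. Nothing in the conduct or analysis would change.

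Much of this stands. The arithmetic is right, no two passages contradict each other, and 0.80 is the end of a range, not the expected power. But non-binding does not mean without effect: the plan says the trial will be halted and allows a permanent stop, with no criteria for that decision. The 0.932 therefore holds only if the interim never ends a trial that would have succeeded. Disclosing 0.17 does not give the reader the loss, because that needs the joint calculation. The countability point would lower power further, so it does not weaken the concern. It is a reason to state the assumption beside the figure.

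**Conclusion.** The concern holds. The 0.932 is correct for a trial that always completes 57 evaluable subjects, but it is presented as the trial's power with no mention of a halt rule that is met with probability 0.17 at the design ORR. Power at 27% runs from 0.932 if no halt ends the trial to 0.803 if every halt is final, a difference of 0.130.

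The lower figure rests on two assumptions: a stopped trial counts as not significant, and all eventual confirmed responses among the first 20 are known at the interim. Relaxing the first raises it (0.828 at an assumed 29 evaluable subjects); relaxing the second lowers it. The 0.130 is thus the loss under those assumptions and not a strict maximum. Type I error is not at risk. This is an incomplete statement of power that should be corrected; it does not invalidate the design or the primary test.

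**What to change.** In protocol 9.7.2, the synopsis (Sample Size Rationale) and SAP 4, state the power as:

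> Power at an ORR of 27% is 0.93 if an interim halt never ends the trial and 0.80 if every halt is final (a stopped trial counted as not significant, and all responses among the first 20 known at the interim).

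The sample size, critical value, test and interim rule all stay as they are. The cost is one sentence in three places and a less favourable stated power. The 0.80 describes an extreme that the plan does not prescribe, so its assumptions must stay attached to it.
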